## **II. Study Objectives, Hypotheses**

**Primary objective:** To evaluate how a structured workshop on pelvic floor disorders impacts decisional conflict with regard to seeking treatment for pelvic organ prolapse and urinary incontinence.

**Secondary objective:** To assess patient satisfaction with the quality of information shared during the workshop, their comfort with discussing pelvic health in a group setting, and the perceived benefits of a nurse continence advisor and psychologist.

### **Hypotheses:**

1. A nurse and psychologist-led workshop on pelvic floor disorders will result in decreased decisional conflict compared to standard individual physician-led counselling.
2. Participants will be satisfied with the quality of information shared and will feel comfortable discussing pelvic health in a group setting

**Primary Outcome & Measure:** Change in "Decisional Conflict" between baseline and follow-up, as measured by the Decisional Conflict Scale.

**Secondary Outcome & Measure:** Participant satisfaction with the group workshop. This will be measured using a survey administered immediately following the workshop

### **III. Study Design and Methodology**

This pilot study will be structured as a randomized control trial in which eligible participants will be recruited at the time of their first urogynecology consultation. Participants will be randomized into two groups: (1) standard care (follow up with urogynecologist as usual) or, (2) a workshop on either urinary incontinence (UI) or pelvic organ prolapse (POP), with a follow-up urogynecologist appointment after attendance at the workshop (Figure 1).

Randomization will be done using a computer generated randomization sequence in blocks of 4 or 6. Sequentially numbered envelopes will contain the randomization result, with the group only revealed at time of randomization. Health care providers will be blinded to the treatment group, but participants will be unblinded to treatment group due to the nature of the intervention.

Patients randomized to the intervention group will be asked to select a workshop on either UI or POP based on which pelvic floor disorder they perceive to be most bothersome. Two identical workshops on different dates will be offered for each topic and participants will be required to attend one to be included in the study.

The workshop will be approximately 90 minutes in length. The first 15 minutes will be an information session on either UI or POP led by a Nurse Continence Advisor. The following 60 minutes will comprise a psychologist-led group discussion. The structured discussion will encourage participants to share experiences, thoughts, and feelings on pelvic floor disorders. Resistances and barriers to seeking treatment will be discussed. Decision-making processes will be explored. During the final 15 minutes, participants will be asked to complete a survey to evaluate the workshop. The survey will assess satisfaction with the information provided, quality of group discussion, comfort level with the group experience, and their satisfaction with the roles of the nurse continence advisor and psychologist.

Using a questionnaire, the following demographics will be collected at baseline: age, marital status, education level, household income, ethnicity, predominant type of pelvic floor dysfunction (urinary incontinence, prolapse, both), and previously attempted treatment modalities. Electronic medical records will also be accessed to confirm the principal diagnosis. The Decisional Conflict Scale (DCS) and the Control Preferences Scale (CPS) will also be administered at the baseline visit.

The DCS is a validated scale that measures (a) perceived uncertainty between treatment options, (b) factors contributing to uncertainty (feeling uninformed, unclear about values, unsupported in decision making), and (c) factors contributing to effective decision making (feeling the choice is informed, values-based, likely to be implemented, and satisfaction with the decision). The CPS is a validated tool that assesses the degree to which patients wish to be involved in treatment decision-making. The CPS is a one-item questionnaire with a five-point scale that describes various degrees of involvement in decision-making. Lower scores on the CPS indicate stronger preferences for an active role in decision making while higher score indicate a preference for a passive or collaborative role.

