##### **Exclusion criteria**

- Anal incontinence
- Previous pelvic radiation therapy
- Non-English speaking
- Requirement for a Substitute Decision Maker
- Inability to attend the workshop
- Unwilling to attend an English-language workshop
- Unwilling to complete English-language surveys

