**Which problem are you MOST concerned about? Please choose ONE only:**

Pelvic organ prolapse   
Urinary incontinence

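### The attendance exclusion is not tied to a topic or date, and the workshop arm picks its topic only after randomisation, so inability to attend can re-emerge in that arm alone

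*Combined protocol and SAP*

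**What the plan says.** Section III recruits eligible women at their first consultation and then randomises them. The topic comes after that: "Patients randomized to the intervention group will be asked to select a workshop on either UI or POP", the choice being made "based on which pelvic floor disorder they perceive to be most bothersome". On dates it says: "Two identical workshops on different dates will be offered for each topic". It then makes attendance at one of these sessions a condition for counting as part of the trial.

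The exclusion list in section IV contains "Inability to attend the workshop". It does not say which topic, which date or how many dates this refers to.

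The Baseline Questionnaire in the Appendix already holds a forced choice between prolapse and incontinence: "Which problem are you MOST concerned about? Please choose ONE only". Nothing restricts it to one arm. Section III also collects at baseline the "predominant type of pelvic floor dysfunction (urinary incontinence, prolapse, both), and previously attempted treatment modalities", and adds: "Electronic medical records will also be accessed to confirm the principal diagnosis". The readable text does not say that any of these answers sets the workshop topic.

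**The concern.** Screening for ability to attend is useful in a trial like this because it takes place before allocation and so affects both arms alike. That protection works only if the question asked at screening is the one that will matter later. Here there is no single workshop to be able to attend. There are four sessions, two per topic, and the pair that applies to a woman depends on a choice that section III places after randomisation.

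A woman who is free only on a prolapse date can pass screening, be allocated to the workshop, select incontinence, and be unable to make either session. A woman recruited after a topic's first session has one date left for it, and after its second she has none. The readable text does not link the exclusion to the dates that remain.

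Because section III makes attendance a condition of inclusion, such a woman leaves the workshop arm. A control with identical availability is never tested in this way and stays. The result is a post-randomisation exclusion on one side only, in a pilot planning 20 to 40 women per arm.

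**Working it through.** **The plan's own figures.** Sample size section: 80 recruited, with at least 50% participating. 80 × 0.50 = 40 and 80 × 1.00 = 80 in total, so 20 to 40 per arm, as stated. The Abstract gives 5 to 10 women per workshop. With 2 topics × 2 dates, capacity is 20 to 40 places, which matches the planned arm size.

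**Sequence in the text.** (1) Eligibility is judged, including ability to attend. (2) The woman is randomised. (3) In the workshop arm only, a topic is chosen and with it two dates. (4) In that arm only, attendance at one session is required for inclusion. Step 1 cannot settle step 4 unless the criterion is defined by topic.

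**Size under each reading of the criterion.** The documents give no availability figure. Assume a woman can make any given date with probability *a*, independently across dates, with all four dates open.

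Free on any one of four dates:
- *a* = 0.7: passes screening 1 − 0.3⁴ = 0.992; free on at least one of her topic's two dates 1 − 0.3² = 0.91; unable to attend given that she passed 1 − 0.91/0.992 = 8.3%.
- *a* = 0.5: 1 − 0.5⁴ = 0.9375; 1 − 0.5² = 0.75; 1 − 0.75/0.9375 = 20%.

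Free on at least one date for each topic:
- *a* = 0.7: passes 0.91² = 83%; unable to attend 0%.

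Free on all four dates:
- *a* = 0.7: passes 0.7⁴ = 24%; unable to attend 0%.

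**In women.** At 8.3%: 0.083 × 20 = 1.7 and 0.083 × 40 = 3.3. At 20%: 4 and 8. At 0%: none.

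The loss therefore ranges from nothing to 20% over these readings and assumed values. The readings also admit very different populations (99%, 83% or 24% of women at *a* = 0.7), and the text does not tell the coordinator which to use.

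**The case against.** The strongest reply is that this is a gap in wording. The documents do not say that the dates are unknown at screening. All four could be shown to each woman, and a woman with no date left would meet the exclusion. Figure 1, the study flowchart, could not be read and may show the order of steps. The one-sided loss also depends on the rule that attendance is required for inclusion. That rule is a separate issue and would remove women who miss the workshop for any other reason.

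Much of this stands. Late disclosure of dates cannot be asserted, and the fix here does not cure the attendance rule. But showing four dates does not say how many, or which, a woman must be able to make, and section III does place the topic choice after allocation.

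A reader might be tempted by three stronger readings, which the documents do not support:

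- **That controls have no matching topic.** The Baseline Questionnaire asks for one problem of most concern without limit by arm, which is close to the rule used to select a workshop. Predominant disorder and principal diagnosis are recorded as well.
- **That the trial lacks a like-for-like control group for each workshop.** The hypotheses and the Analysis of results section compare workshop with control overall, and no comparison by topic is planned. An even split would leave only 10 to 20 women per topic in each arm.
- **That up to 13 women in an arm of 40 would be lost.** This takes *a* = 0.5 with one date left per topic for the whole arm: 1 − 0.5/0.75 = 33%, and 0.33 × 40 = 13. The remaining 27 would need places, but two sessions of at most 10 hold 20. It also takes the loosest reading of the criterion and independent dates. Positive correlation in a woman's availability lowers the loss, to zero if it is perfect.

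**Conclusion.** The point holds as a defect in how the attendance criterion is defined and timed. As written, a woman can satisfy eligibility and still be unable to attend either session for her topic, and the consequence falls on the workshop arm alone. The frequency is not derivable from the documents. It is zero if the criterion is applied per topic, and about 8% if any one of four dates suffices, at an assumed 0.7 per date with independence and all four dates open. These figures illustrate what the wording allows and are not a forecast. The primary overall comparison does not need a topic for controls, so nothing in the case rests on results by topic. The change is worth making before recruitment because it is cheap and removes one avoidable source of one-sided exclusion.

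**What to change.** In section III, state that every woman completes the baseline question on her problem of most concern before the envelope is opened, and that this answer sets her workshop topic. In the exclusion criteria, define inability to attend as not being free on any remaining date for that topic, and apply it to all women before allocation. State that randomisation of women for a topic stops once its last session has passed. Record the dates checked on the screening form.

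This means rewording two sections and adding one dated screening entry. It needs no new questionnaire and leaves the planned 40 to 80 participants unchanged. The real cost is screen failures. Compared with an any-of-four rule, they rise from 0.8% to 9% at *a* = 0.7 and from 6.25% to 25% at *a* = 0.5; with one date left per topic and *a* = 0.5, from 25% to 50%. Compared with a one-date-per-topic rule they fall, from 17% to 9% at *a* = 0.7. Since the sample size rests on clinic volume, recruitment should be checked against this.

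Results by baseline topic and arm may be shown as optional description. A woman who later changes her mind would stay under her baseline topic there. The attendance-for-inclusion rule needs its own resolution.

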## **Abstract**

Pelvic floor disorders can significantly affect a woman's quality of life, yet many feel uncomfortable openly discussing these topics. Treatments include lifestyle modification, medications, and/or surgery. Decisional conflict arises when patients have difficulty choosing between several viable treatment options. Factors contributing to decisional conflict include biased information, poor peer support, and unaddressed fears. Effective counselling may help address these factors. Objectives of this pilot study are to assess: (1) the impact of a small-group workshop on pelvic floor disorders (urinary incontinence (UI), or pelvic organ prolapse (POP)) on decisional conflict regarding treatment options; and (2) participant satisfaction with the workshop in terms of quality of information shared, comfort with discussing pelvic health in a group setting, and perceived benefits of a nurse continence advisor and psychologist. Women  $\geq$  18 years old with urinary incontinence or pelvic organ prolapse will be randomized at the time of their first urogynecology consultation to usual care or a 90 minute workshop on either UI or POP. Five to 10 women will attend each workshop led by a nurse continence advisor and a psychologist. In both groups, decisional conflict will be measured using the validated Decisional Conflict Scale (DCS) at baseline and at the first follow-up clinic appointment. Satisfaction with the workshop will be assessed by a post-workshop survey. Demographic data will be compared between groups using t-tests for continuous data and chi-square tests for categorical data. Change in DCS score will be compared using t-tests. Linear regression analysis will be performed to identify predictors of decisional conflict. This pilot study will assess the feasibility and acceptability of an educational workshop on pelvic floor disorders and its potential impact on decisional conflict. Results of this study will inform future development of interdisciplinary, patient-centred approaches to enhanced decision making in women's health.

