#### **IV. Study Population/Recruitment/Consent process**

##### **Sample size**

For this pilot study, we estimate that recruiting a total of 80 participants will be feasible based on the volume of new consults to the Riverside Hospital Urogynecology Clinic. With a minimum 50 percent participation rate, this would result in a total sample size of 40-80 participants (20-40 per study group).

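### Two sessions per self-chosen topic match the planned 20-40 workshop women in total, but leave no margin for uneven topic choice near the top, and the attendance rule would drop unseated women from one arm only

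*Combined protocol and SAP*

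**What the plan says.** Section III (Study Design and Methodology) fixes the number of sessions: "Two identical workshops on different dates will be offered for each topic". There are two topics, urinary incontinence (UI) and pelvic organ prolapse (POP), so four sessions in all. Women already randomised to the workshop are "asked to select a workshop on either UI or POP based on which pelvic floor disorder they perceive to be most bothersome". The same section adds that "participants will be required to attend one to be included in the study".

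Session size appears only in the Abstract: "Five to 10 women will attend each workshop led by a nurse continence advisor and a psychologist". The Sample size section says "we estimate that recruiting a total of 80 participants will be feasible based on the volume of new consults", assumes that at least half take part, and arrives at 40-80 women in total, or "20-40 per study group".

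The protocol does not say what happens if a topic is oversubscribed or underfilled. The analysis section specifies unpaired t-tests on decisional conflict scores and does not say how randomised women who do not attend are handled.

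**The concern.** The number of sessions is fixed by topic, but demand for each topic is set by the women after randomisation. Places left over in the POP sessions are no use to a woman who wants the UI workshop. Total capacity can therefore equal the planned arm size while one topic is over-full and the other has empty seats.

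A woman without a seat cannot attend, and under the attendance rule she is then not included. Controls face no such filter. The losses would fall on one arm only and would come from whichever topic is more popular. That costs precision and weakens the randomised comparison of change in the Decisional Conflict Scale (DCS), the primary outcome, for a purely logistical reason.

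**Working it through.** **Inputs.** From the protocol: 2 topics, 2 sessions per topic, 5-10 women per session, recruitment of 80, participation of at least 50%, two groups. Not in the protocol: the share of women preferring each topic. I take 50, 60 and 70% for one topic as assumptions.

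**The plan's own figures.** Arm size: 80 × 0.50 / 2 = 20 and 80 × 1.00 / 2 = 40. Workshop places: 2 × 2 × 5 = 20 and 2 × 2 × 10 = 40. The two ranges agree.

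**Limit per topic.** 2 × 5 = 10 to 2 × 10 = 20 women.

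**Seating.** Let n be the number of workshop women and X the number choosing UI, with X ~ Binomial(n, p). Everyone is seated if X ≤ 20 and n − X ≤ 20, that is, n − 20 ≤ X ≤ 20. The mean number unseated is E[max(0, X − 20) + max(0, n − X − 20)]. At n = 40 the only acceptable value is X = 20, so at p = 0.5 the probability is C(40,20) × 0.5^40 = 0.125.

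| n | X that seats everyone | P(all seated), p = 0.5 / 0.6 / 0.7 | Mean unseated |
|---|---|---|---|
| 20 | any | 1.00 / 1.00 / 1.00 | 0 |
| 26 | 6-20 | 0.998 / 0.979 / 0.837 | not computed |
| 30 | 10-20 | 0.957 / 0.823 / 0.411 | 0.07 / 0.34 / 1.58 |
| 36 | 16-20 | 0.595 / 0.331 / 0.047 | 0.89 / 2.17 / 5.24 |
| 40 | 20 only | 0.125 / 0.055 / 0.004 | 2.51 / 4.29 / 8.01 |

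At n = 40 the mean loss as a share of the arm is 2.51/40 = 6%, 4.29/40 = 11% and 8.01/40 = 20%.

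**Lower end.** At n = 20 all four sessions reach 5 only at 10/10: probability 0.18 / 0.12 / 0.03. The consequence is a small session, not a lost place. If a topic may run one session instead of two, an arm of 20 fits within 5-10 with probability 0.99 / 0.95 / 0.76.

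**Dates.** The table assumes that women can be spread freely over the two dates of their topic. If instead they choose the date as well, with topic and date both at an assumed 50/50, the probability that all four sessions fall within 5-10 is 0.47 at n = 30 and 0.004 at n = 40. That count includes sessions that are too small as well as too full.

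**The case against.** A reader might infer that the stated arm size cannot be delivered at all. The documents do not support that. The plan gives a range, total places equal that range, and arms up to about 30 mostly fit unless preference is strongly skewed. Forty per arm also needs all 80 women to take part, whereas the plan only assumes at least half.

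A reader might also put the lower end on the same footing as the upper, since 20 women fill all four sessions to 5 only at 10/10. That does not follow either: nobody is turned away at 20, and the protocol does not say that a session of fewer than five is cancelled.

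Two further points carry weight. The 5-10 figure stands only in the Abstract and may describe an expectation; Section III sets no maximum and does not rule out further sessions. If the figure is soft, the 2.5 extra women expected at 40 with even preference could be absorbed by slightly larger groups. And the one-sided exclusion comes from the attendance rule, which would operate on any non-attender whatever the seating.

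These points limit the concern but do not remove it. If 5-10 is not a limit, the protocol should say so. If it is a limit, the upper part of the range rarely fits. In both cases the attendance rule turns a seating problem into a loss from one arm, and it needs correcting in its own right.

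**Conclusion.** The concern holds for the upper part of the range. Under the plan's own session numbers, an arm of 40 seats everyone with probability 0.125 at best among the shares examined, and an arm of 36 with probability 0.60 at best. At 30 the probability is 0.96 or 0.82 for preferences of 50 or 60%, but only 0.41 at 70%.

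This rests on three assumptions: that 10 per session is a firm maximum, that the preference shares are as assumed, and that women can be moved between the two dates of their topic. The last is favourable to the plan. The direction and size of any bias in the DCS comparison cannot be worked out from the documents; what can be said is that losses would be confined to the workshop arm and selected by topic.

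**What to change.** 1. Replace the attendance rule. Every randomised woman, including one who cannot be seated, is followed up and analysed for change in DCS in her assigned arm. An analysis of attenders only may be kept as secondary. The Abstract already plans the DCS for both groups at baseline and at the first follow-up appointment, so no new visit is needed.

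2. Settle the status of the 5-10 figure. Either state that it is a target that may be exceeded, or restate the upper workshop-arm size that two sessions per topic can reliably seat as about 30 (2 × 30 = about 60 randomised), giving the assumed preference shares alongside.

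Optionally, set the topics of the four sessions by demand, using the baseline question on which problem concerns the woman most. At 30 women this raises the probability that every session held has 5-10 women from 0.957 / 0.823 / 0.411 to 1.000 / 0.998 / 0.970. It does not rescue 40 (0.127 / 0.075 / 0.117), and it may leave one topic with a single date, so it is a trade-off and not a requirement.

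The cost is protocol wording. Including non-attenders dilutes the effect estimate slightly, and the stated upper size looks less favourable if it is cut to about 30 per arm.

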There are few studies on how decision coaching can help women with prolapse and incontinence reach a satisfactory decision about treatment. This study aims to use the principals of shared decision making to address decisional conflict surrounding treatment for pelvic floor disorders. Specifically, we will evaluate the feasibility and acceptability of small group workshops on pelvic organ prolapse and urinary incontinence led by a nurse continence advisor and a psychologist (decision coach). We will also assess impact of the workshop on decisional conflict. Results of this study will inform future development of interdisciplinary, patient-centered approaches to enhanced decision making in women’s health.

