#### **Analysis of results**

Baseline socio-demographic data will be compared between groups using t-tests for

continuous data and chi-square tests for categorical data. Differences in decisional conflict scores between the intervention and control groups will be compared using unpaired t-tests. Linear regression will be done to identify significant predictors of decisional conflict in this population.

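### Women allocated to the workshop count in the study only if they attend, controls face no such condition, and no all-randomised analysis set is named, so the primary DCS comparison can be biased

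*Combined protocol and SAP*

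**What the plan says.** The Abstract states that women "will be randomized at the time of their first urogynecology consultation to usual care or a 90 minute workshop", so attendance is always a post-randomisation event. In Section III, Study Design and Methodology, the paragraph on the workshop arm opens "Patients randomized to the intervention group will be asked to select a workshop on either UI or POP". It offers two dates per topic and ends "participants will be required to attend one to be included in the study". Controls have usual urogynecology follow-up and no comparable condition.

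Under Analysis of results, the comparison is described as "Differences in decisional conflict scores between the intervention and control groups will be compared using unpaired t-tests". Neither that section nor any other mentions an intention-to-treat or all-randomised set, a per-protocol set, or the handling of women who do not attend.

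Three other places bear on the point:

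- The Abstract plans the DCS in both groups "at baseline and at the first follow-up clinic appointment".
- The Exclusion criteria remove women who cannot attend a workshop, and also those "Unwilling to attend an English-language workshop".
- Section I promises that "we will evaluate the feasibility and acceptability of small group workshops", but attendance is not among the outcomes listed in Section II.

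**The concern.** Randomisation makes the two arms comparable as allocated. Removing non-attenders from one arm undoes that, because the controls who would have stayed away cannot be identified and remain in the comparison. A difference in DCS change could then partly reflect who came. The direction cannot be predicted: attenders may be more engaged and improve more, or may start with less conflict and have less room to improve.

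The affected comparison is the primary objective, the first hypothesis and the primary outcome. If non-attenders leave before the follow-up DCS, no later reanalysis can restore the comparison as randomised. Dropping them would also hide attendance, which is a central feasibility result for a pilot of this kind.

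**Working it through.** **The plan's own figure.** Under Sample size, 80 women at 50% to 100% participation gives 80 × 0.5 = 40 up to 80, or 20 to 40 per group. Workshop capacity agrees: 2 topics × 2 dates × 5 to 10 women = 20 to 40. The stated range reproduces. It has no allowance specific to loss in the workshop arm, and it does not say whether participation means consent or attendance.

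**Size of the bias.** Let *a* be the proportion of the workshop arm that attends, and *d* the mean DCS change of would-be attenders minus that of would-be non-attenders, in SD units. With no workshop effect:

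- workshop arm as analysed: mean of attenders, μ_A
- control arm: *a*·μ_A + (1 − *a*)·μ_N
- difference: (1 − *a*)(μ_A − μ_N) = (1 − *a*)·*d*

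The documents give neither *a* nor *d*; both are assumed below.

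**Effect on type I error.** This was simulated with 200,000 runs per cell: 40 randomised per arm, within-stratum SD 1, no workshop effect, workshop arm reduced to attenders, all 40 controls kept, pooled two-sided t-test at an assumed 5%. Entries are for *d* = 0.2 / 0.3 / 0.5.

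| Attendance | Analysed (workshop vs control) | Bias, SD | Type I error, % |
|---|---|---|---|
| 90% | 36 vs 40 | 0.02 / 0.03 / 0.05 | 5.1 / 5.2 / 5.6 |
| 80% | 32 vs 40 | 0.04 / 0.06 / 0.10 | 5.3 / 5.7 / 6.9 |
| 70% | 28 vs 40 | 0.06 / 0.09 / 0.15 | 5.6 / 6.4 / 8.9 |
| 50% | 20 vs 40 | 0.10 / 0.15 / 0.25 | 6.4 / 8.2 / 14.0 |

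With 20 randomised per arm, the rates are 5.0 / 5.3 / 5.9% at 80% attendance and 5.6 / 6.4 / 9.0% at 50%.

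**Cross-check by normal approximation**, with SE = √(1/(*an*) + 1/*n*). For *n* = 40, *a* = 0.8, *d* = 0.5: bias = 0.2 × 0.5 = 0.10; SE = √(1/32 + 1/40) = 0.237; bias/SE = 0.42; rejection probability about 7.1%, against 6.9% simulated. A larger gap matters more: at 60% attendance and *d* = 1.0 the bias is 0.40 SD and the rate is 19.5% (20 per arm) to 34.1% (40 per arm).

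**For scale.** The difference detectable with 80% power is about 0.63 SD at 40 per arm and 0.89 SD at 20 per arm.

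**Numbers analysed.** If the lower figure of 20 means women allocated to the workshop, all 20 attend with probability 0.9^20 = 12% at 90% attendance and 0.8^20 = 1% at 80%; the expected numbers analysed are 18 and 16. This does not apply if 20 is already a count of attenders.

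**After correction.** If all randomised women are analysed as allocated with complete follow-up DCS, this bias term is zero for any *a* and *d*, and type I error returns to 5%.

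**The case against.** The strongest reply is that the effect is probably small. Women unable or unwilling to attend are excluded before randomisation, two dates per topic are offered, and parking is reimbursed. If 80% to 90% attend, the assumed bias is at most 0.10 SD and type I error at most 6.9%, in a pilot sized on feasibility. That is correct, and it limits the likely size. It does not remove the problem: those screens act on declared ability and willingness, not on women who are randomised and then do not come. Pilot status does not help either, since the primary objective is the between-group comparison.

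Second, the sentence could mean a commitment asked at enrolment. Its placement, among instructions for women already allocated to the workshop, points the other way, and no passage keeps non-attenders in the t-test. On either reading the text needs an edit. The study flowchart (Figure 1) was not legible in the text reviewed; if it shows follow-up of non-attenders, it conflicts with this sentence and the two must be reconciled.

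Third, if 50% participation means attendance, the 20 to 40 per group already allows for loss, though equally in both arms. That stands, so the numbers-analysed figures are conditional and peripheral.

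Fourth, Section III places the workshop arm's follow-up appointment after attendance, so a non-attender has no clear follow-up time there, and a t-test of change cannot include women without a follow-up DCS. Both points stand and belong in the correction.

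**Conclusion.** The concern holds and the text is wrong as written. Inclusion depends on a post-randomisation event in the workshop arm only, and nothing elsewhere in the plan restores the non-attenders. Under assumed gaps of 0.2 to 0.5 SD the distortion is small when nearly all attend and material when about half do. The plan gives no attendance figure that settles where in that range the trial will fall, and the sign is unknown. It should be corrected before follow-up data are collected, because the loss cannot be repaired afterwards.

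**What to change.** 1. **Section III.** Delete the attendance condition and write: *Women allocated to the workshop will be asked to come to one of the two sessions on their topic. Every randomised woman stays in the study whether or not she attends.* If a commitment before randomisation was intended, state it in the eligibility criteria so that it applies to both arms.
2. **Analysis of results.** Add: *The primary comparison of change in DCS includes all randomised women in their allocated group; any comparison restricted to attenders is secondary.* State how a missing follow-up DCS will be handled.
3. **Follow-up.** Apply the follow-up DCS planned in the Abstract to non-attenders too, and align the Section III phrase that ties follow-up to attendance.
4. **Outcomes.** Report the number and proportion attending as a feasibility result.
5. **Sample size.** Say whether 50% participation means consent or attendance, and give numbers randomised and analysed by arm.

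The cost is mainly a wording amendment, plus the effort of obtaining the DCS from non-attenders. The statistical downside is dilution. If non-attenders gain nothing, the all-randomised effect is 0.8 times the attender effect at 80% attendance and 0.5 times at 50%. With 40 per arm and 80% power, detecting 0.634 SD overall then requires 0.634/0.8 = 0.79 SD or 0.634/0.5 = 1.27 SD among attenders. The change buys validity, not power.
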